| STUDY DESIGN | This is a randomized, multi-site double-blind placebo-controlled trial of melatonin 3 mg vs. 6 mg vs. placebo orally nightly for migraine prevention in adolescents. We will use a “remote trial” design, wherein after the initial in-person enrollment visit all study procedures will be done from the comfort of the participant’s own home. We intend to enroll approximately 210 participants over 24-30 months at two sites: UCLA and UCSF. |
| PRIMARY OBJECTIVE | 1. To compare the number of migraine/migrainous days in the 5th-8th weeks of randomized treatment between melatonin (combined 6mg + 3mg) vs. placebo. |

| | |
|-----------------------------------|--|
| SECONDARY OBJECTIVES | 
 1. To compare the number of migraine/migrainous days in the 5th-8th weeks of randomized treatment between melatonin 3 mg vs. placebo. 2. To compare the number of migraine/migrainous days in the 5th-8th weeks of randomized treatment between melatonin 6 mg vs. placebo. 3. To compare the number of migraine/migrainous days in the 5th-8th weeks of randomized treatment between melatonin 3 mg vs. 6 mg. 4. To compare the mean headache days in 5th-8th randomized phase in melatonin (combined) vs. placebo, (followed by melatonin 3 mg vs. placebo, melatonin 6 mg vs. placebo, and melatonin 3 mg vs. melatonin 6 mg using t-tests). 5. To compare the mean acute medication use days in 5th-8th randomized phase in melatonin (combined) vs. placebo, (followed by melatonin 3 mg vs. placebo, melatonin 6 mg vs. placebo, and melatonin 3 mg vs. melatonin 6 mg using t-tests). 6. To compare the mean PedMIDAS score (continuous) in 5th-8th randomized phase in melatonin (combined) vs. placebo, (followed by melatonin 3 mg vs. placebo, melatonin 6 mg vs. placebo, and melatonin 3 mg vs. melatonin 6 mg using t-tests). 7. To compare the number of $\geq 50\%$ responder rate in 5th-8th randomized phase in melatonin (combined) vs. placebo (Chi-square or Fisher's exact (if needed), (followed by melatonin 3 mg vs. placebo, melatonin 6 mg vs. placebo, and melatonin 3 mg vs. melatonin 6 mg using Chi-square (or Fisher's exact)). |
| NUMBER OF SUBJECTS | Approximately 210 subjects |

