3.2 Secondary Objectives

1. To compare the number of migraine/migrainous days in the 5th-8th weeks of randomized treatment between **melatonin 3 mg vs. placebo**.
2. To compare the number of migraine/migrainous days in the 5th-8th weeks of randomized treatment between **melatonin 6 mg vs. placebo**.
3. To compare the number of migraine/migrainous days in the 5th-8th weeks of randomized treatment between **melatonin 3 mg vs. 6 mg**.
4. To compare the mean headache days in 5th-8th randomized phase in melatonin (combined) vs. placebo, (followed by melatonin 3 mg vs. placebo, melatonin 6 mg vs. placebo, and melatonin 3 mg vs. melatonin 6 mg using t-tests).
5. To compare the mean acute medication use days in 5th-8th randomized phase in melatonin (combined) vs. placebo, (followed by melatonin 3 mg vs. placebo, melatonin 6 mg vs. placebo, and melatonin 3 mg vs. melatonin 6 mg using t-tests).
6. To compare the mean PedMIDAS score (continuous) in 5th-8th randomized phase in melatonin (combined) vs. placebo, (followed by melatonin 3 mg vs. placebo, melatonin 6 mg vs. placebo, and melatonin 3 mg vs. melatonin 6 mg using t-tests).
7. To compare the number of $\geq 50\%$ responder rate in 5th-8th randomized phase in melatonin (combined) vs. placebo (Chi-square or Fisher's exact (if needed),

(followed by melatonin 3 mg vs. placebo, melatonin 6 mg vs. placebo, and melatonin 3 mg vs. melatonin 6 mg using Chi-square (or Fisher's exact)).

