5.2 Secondary Efficacy Endpoints

1. Mean migraine/migrainous days in weeks 5-8 of randomized treatment phase in melatonin 6 mg vs. placebo.
2. Mean migraine/migrainous days in weeks 5-8 of randomized treatment phase in melatonin 3 mg vs. placebo.
3. Mean migraine/migrainous days in weeks 5-8 of randomized treatment phase in melatonin 6 mg vs. melatonin 3 mg.
4. Change in mean migraine/migrainous days from weeks 5-8 of single-blind treatment phase to weeks 5-8 of randomized treatment phase for each group.
5. Mean PedMIDAS (headache related disability score) in weeks 5-8 of randomized treatment phase in melatonin treated group vs placebo, and in each of the three pair-wise group comparisons.
6. Mean CASQ score in weeks 5-8 of randomized treatment phase in melatonin treated group vs. placebo, and in each of the three pair-wise group comparisons.
7. Number of days acute medication is used in weeks 5-8 of randomized treatment phase in melatonin treated group vs. placebo, and in each of the three pair-wise group comparisons.
8. Number of headache days in weeks 5-8 of randomized treatment phase in melatonin treated group vs. placebo, and in each of the three pair-wise group comparisons.

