10 EVALUATIONS BY VISIT

10.1 Visit 1 (Screening and Enrollment, Day 1)

We will do a one-time enrollment visit at either UCSF or UCLA.

Consent/assent: At the start of an enrollment visit, potential subjects and their parent/guardian will be told about the study by a study investigator and/or study coordinator and will be provided with an informed consent document to review. For 12-17 year-olds, the informed consent document is addressed to the adolescent and is to be signed by both the adolescent and their parent/guardian. For 10-11 year-olds, the parent will sign the consent form and the participant will be provided with a simplified assent document. For this group the participant's assent will be documented by a study team member. Participants and parents/guardians will be given the opportunity to ask questions and have them answered to their satisfaction before deciding whether to participate. Consent and HIPPA can be signed with paper/pen or via DocuSign.

Enrollment visit data:

The enrollment visit data will be entered directly into the study database during the enrollment visit. Demographic and logistical information will be collected including name, age, sex, race/ethnicity, shipping address, participant smartphone number, parent smartphone number, and best times for follow-up calls. A pediatric headache neurologist will review the headache history to ensure the participant meets ICHD criteria for migraine with or without aura and will review the current medication list and past medical history. We will measure weight, blood pressure, pulse, and respiratory rate. There will be a general medical examination and a neurologic examination. Girls who have had their first period will undergo a urine pregnancy test. Baseline assessment of the PedMIDAS score and CASQ score will be assessed. Participants will be taught how to use the headache diary on their smartphone. They will be given the study medication for the single-blind placebo treatment phase and instructed to take study medication 1 hour before bedtime.

10.2 8-week single-blind placebo treatment phase (Weeks 1-8):

Participants will take the study medication nightly and complete a headache diary nightly. A text message will be sent from the study database each evening to remind them to do

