14.3 Analysis of Primary Endpoint

Primary outcome: Number of migraine/migrainous days in the 5th-8th weeks of randomized treatment between melatonin (combined 6 mg+3mg) vs. placebo. We will control for baseline migraine/migrainous day frequency in the 5-8th week of the single-blind treatment phase and use an ANCOVA analysis.

Definition of migraine/migrainous day:

- 1) Patient had a moderate or severe headache and took a migraine-specific medication (triptan or ergot)
- 2) Patient had a moderate or severe headache; headache lasted for at least 2 hours, and
 - a. At least one of the following was present (throbbing quality, movement sensitivity, or unilateral/bilateral location) AND
 - b. At least one of the following was also present (photophobia, phonophobia, nausea or vomiting)

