14.4 Analysis of Secondary Endpoints

Secondary outcome measures will include $\geq 50\%$ responder rates, tolerability (as measured by CASQ scores), and need for use of acute headache medications. Safety and tolerability data will be summarized by treatment group. Adverse event rates will be coded by body system. Adverse events will be tabulated by treatment group and will include the number of patients for whom the event occurred, the rate of occurrence, and the severity and relationship to study drug.

Secondary outcomes:

(We will control for the baseline level of these outcomes in all of these analyses)

Effectiveness secondary outcomes:

1. Number of migraine/migrainous days in the 5th-8th weeks of randomized treatment between **melatonin 3 mg vs. placebo**.

2. Number of migraine/migrainous days in the 5th-8th weeks of randomized treatment between **melatonin 6 mg vs. placebo**.
3. Number of migraine/migrainous days in the 5th-8th weeks of randomized treatment between **melatonin 3 mg vs. 6 mg**.
4. Mean headache days in 5th-8th randomized phase in melatonin (combined) vs. placebo, (followed by melatonin 3 mg vs. placebo, melatonin 6 mg vs. placebo, and melatonin 3 mg vs. melatonin 6 mg using t-tests).
5. Mean acute medication use days in 5th-8th randomized phase in melatonin (combined) vs. placebo, (followed by melatonin 3 mg vs. placebo, melatonin 6 mg vs. placebo, and melatonin 3 mg vs. melatonin 6 mg using t-tests).
6. Mean PedMIDAS score (continuous) in 5th-8th randomized phase in melatonin (combined) vs. placebo, (followed by melatonin 3 mg vs. placebo, melatonin 6 mg vs. placebo, and melatonin 3 mg vs. melatonin 6 mg using t-tests).
7. $\geq 50\%$ responder rate in 5th-8th randomized phase in melatonin (combined) vs. placebo (Chi-square or Fisher's exact (if needed), (followed by melatonin 3 mg vs. placebo, melatonin 6 mg vs. placebo, and melatonin 3 mg vs. melatonin 6 mg using Chi-square (or Fisher's exact)).

Safety outcomes:

1. Proportion with adverse events between groups
 - a. Proportion with serious adverse events between groups
 - b. Proportion of adverse events thought to be related to the study treatment
2. Mean Sleepiness score in 5th-8th randomized phase in melatonin (combined) vs. placebo, (followed by melatonin 3 mg vs. placebo, melatonin 6 mg vs. placebo, and melatonin 3 mg vs. melatonin 6 mg using t-tests).

Trial design assessment outcome:

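### Section 14.4 promises baseline control in every secondary analysis but names t-tests, with no adjusted model, for nine pairwise comparisons of headache days, acute-medication days and PedMIDAS

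*Combined protocol and SAP*

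**What the plan says.** Under the secondary outcomes in section 14.4, and again at the end of the secondary endpoints in the synopsis, the plan states: "We will control for the baseline level of these outcomes in all of these analyses".

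Items 4, 5 and 6 of the section 14.4 list (headache days, acute-medication days, PedMIDAS) each give a pooled comparison with placebo, followed by "melatonin 3 mg vs. placebo, melatonin 6 mg vs. placebo, and melatonin 3 mg vs. melatonin 6 mg using t-tests". The synopsis endpoints use the same wording. The secondary objectives, in the synopsis and in section 3.2, also name the t-tests but do not carry the baseline sentence.

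An adjusted model is named for one outcome only. For the primary endpoint, section 14.3 says: "We will control for baseline migraine/migrainous day frequency in the 5-8th week of the single-blind treatment phase and use an ANCOVA analysis". The other places that mention ANCOVA (the synopsis and section 3.1) also concern the primary outcome.

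Two neighbouring items are less clear:

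- **Sleepiness.** Section 5.2 lists it as a secondary efficacy endpoint ("Mean CASQ score in weeks 5-8 of randomized treatment phase in melatonin treated group vs. placebo"), and the opening of section 14.4 also counts CASQ among the secondary measures. The synopsis and the later list in section 14.4 put the sleepiness score under safety, again with t-tests.
- **Responder rate.** Item 7 ends with "and melatonin 3 mg vs. melatonin 6 mg using Chi-square (or Fisher's exact".

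**The concern.** The plan gives two instructions for the same nine comparisons. One requires baseline control. The other names a test that, in its ordinary meaning, compares two sets of on-treatment values and contains no covariate. Nothing in the documents says which prevails or how they combine.

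Both analyses are legitimate in a randomised trial, so the danger is not bias in either one. The danger is that the choice stays open. An analyst could run the adjusted or the unadjusted version and settle on one after seeing both. If the t-tests are run as written, the plan's own commitment is broken and information from baselines the trial already collects is thrown away.

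The responder rate is a separate and smaller matter. An indicator of at least 50% response has no baseline level of its own, so the baseline sentence does not fit item 7. That is a problem with the scope of the sentence, not a missing adjustment.

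**Working it through.** **Count of affected tests**

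- Outcomes with t-tests named in items 4 to 6: 3. Pairwise contrasts for each: 3. Total 3 × 3 = 9.
- Sleepiness adds 3, giving 12 if the baseline sentence covers it. The position of the sentence does not settle this: in section 14.4 it stands above both the effectiveness and the safety lists, while in the synopsis it closes the secondary endpoints, before the safety outcomes begin.
- Items 1 to 3 (pairwise migraine-day comparisons) name no test, and for the pooled comparisons in items 4 to 6 it is unclear whether any test is named. Neither group is counted.
- Item 7 has 1 pooled and 3 pairwise tests, 4 in all, kept apart as a scope mismatch.

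**The plan's own sample-size figure**

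Section 14.6 gives a difference of 1.1 days, SD 1.8 and 42 per arm with outcome data. The significance level and power are not stated; I assume two-sided 0.05 and 80%. Then n = 2 × (1.960 + 0.842)² × 1.8² / 1.1² = 42.03 per arm, so 42 is reproduced (43 if rounded up). No baseline adjustment enters this figure, and the present point does not depend on it. I use 42 per arm only to judge the cost of estimating a slope. The plan's attrition assumptions give slightly more, 70 × 0.75 × 0.85 = 44.6 per arm, which makes no material difference.

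**What adjustment is worth**

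Let ρ be the within-arm correlation between an outcome and its baseline. The documents give no ρ, SD or effect for these three outcomes, so ρ is an assumption shown over a range and no power figure is claimed.

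- Gross variance ratio, unadjusted to ANCOVA: 1/(1 − ρ²).
- Cost of estimating one common slope with 3 arms of 42 (N = 126): 1 + 1/(126 − 3 − 2) = 1 + 1/121 = 1.0083.
- Net ratio: gross ratio / 1.0083.
- Reduction in interval width: 1 − 1/√ratio.

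| Assumed ρ | Gross ratio | Narrower, gross | Net ratio | Narrower, net |
|---|---|---|---|---|
| 0.1 | 1.010 | 0.5% | 1.002 | 0.1% |
| 0.3 | 1.099 | 4.6% | 1.090 | 4.2% |
| 0.5 | 1.333 | 13.4% | 1.322 | 13.0% |
| 0.7 | 1.961 | 28.6% | 1.945 | 28.3% |

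A simulation with normal data and 42 per arm (20,000 runs) gave ratios of 1.000, 1.093, 1.339 and 1.969, in line with the net column. ANCOVA breaks even at ρ = √(1 − 1/1.0083) ≈ 0.09 and gains above that.

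**Which baselines exist**

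The diary outcomes have run-in weeks 5 to 8, the same window used for the primary covariate. For the questionnaires, section 10.1 says "Baseline assessment of the PedMIDAS score and CASQ score will be assessed", at the enrolment visit, and section 10.5 repeats both scores at study completion. Their baseline therefore precedes the eight-week placebo run-in, so ρ for PedMIDAS and CASQ may be lower than for the diary counts.

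**The case against.** **The sentence already governs.** It is explicit and covers every analysis, and a pairwise contrast from an ANCOVA is itself tested with a t statistic. On that reading the plan has only left a model unnamed. The reading is possible, but no section states it. Where the authors wanted ANCOVA they wrote ANCOVA, which makes the t-test wording hard to read as shorthand for it.

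**The t-tests might be on change from baseline.** Section 5.2 does list a change endpoint, but only for migraine days and within each group; items 4 to 6 of section 14.4 name on-treatment means. This would also be a third candidate analysis. With equal variances at the two times, a change score has variance 2(1 − ρ) times the unadjusted variance: 1.4 times at ρ = 0.3, equal at ρ = 0.5, and 0.6 times at ρ = 0.7. Below ρ = 0.5 it is worse than no adjustment, so the choice of reading matters.

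**The gain may be negligible.** At ρ = 0.1 it is about 0.1% of interval width after the slope cost, or nothing, and that is the end of the range where PedMIDAS may lie. This stands. The larger figures illustrate assumed correlations and are not properties of this trial.

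**Narrowing the sentence would also cure the contradiction.** It would: keeping unadjusted t-tests and limiting the promise is coherent and valid. It would, however, withdraw the sponsor's stated intention and discard baselines already collected.

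**These are secondary outcomes, and objectives need not list covariates.** Both are true, and they limit the weight of the point. The missing baseline sentence in the objectives is not an error in itself, but those lists do name the t-tests and so need to be brought into line.

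**Conclusion.** The concern holds. For nine pairwise comparisons (twelve if sleepiness is covered) the plan promises baseline control and names a test that does not provide it. No section reconciles the two.

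The consequence is moderate: analyst discretion on three listed secondary outcomes, plus a loss of precision if the tests are run as written. That loss ranges from essentially none at a correlation of 0.1 to intervals that could have been about 28% narrower at 0.7. Every correlation is assumed; only the 42 per arm comes from the documents.

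No bias is claimed, the unadjusted tests are valid, and the primary analysis is untouched. No loss of precision is claimed for the responder rate. Because the remedy carries out the sponsor's own stated intention without new data, it should be made.

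**What to change.** Amend section 14.4 before unblinding; section 8.2 keeps the blind until after database lock.

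- **Continuous outcomes.** Replace the t-tests in items 4 to 6 with one three-arm ANCOVA per outcome, adjusted for that outcome's own baseline: run-in weeks 5 to 8 for headache days and acute-medication days, and the enrolment score for PedMIDAS. Take the pooled and the three pairwise contrasts from that model.
- **Items 1 to 3.** State that these migraine-day contrasts come from the primary ANCOVA model.
- **Sleepiness.** Say whether the baseline sentence applies. If it does, use the same ANCOVA with the enrolment CASQ score as covariate.
- **Responder rate.** Either limit the baseline sentence to the continuous outcomes and keep the chi-square or Fisher tests, or name a baseline-adjusted model. Both are acceptable.
- **Consistency.** Make the same changes in the synopsis (objectives and endpoints) and in section 3.2.

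The cost is a few sentences. No data, visits or participants are added.

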| OTHER EVALUATIONS | 
Safety outcomes:
 
 1. Proportion with adverse events between groups 
 a. Proportion with serious adverse events between groups b. Proportion of adverse events thought to be related to the study treatment 2. Mean Sleepiness score in 5th-8th randomized phase in melatonin (combined) vs. placebo, (followed by melatonin 3 mg vs. placebo, melatonin 6 mg vs. placebo, and melatonin 3 mg vs. melatonin 6 mg using t-tests). 
Trial design assessment outcome:
 
 1. Proportion of participants on melatonin who correctly guessed they were on it (just playing chance, 66% should guess melatonin) 2. Proportion of participants on melatonin who guessed their dose correctly (by chance 50% 3 mg, 50% 6 mg). 3. Proportion of participants on placebo who correctly guessed they were on placebo (by chance, 33% should guess this) 4. The same three above but with investigators guessing. |
| SAFETY EVALUATIONS | Incidence of adverse events |
| PLANNED INTERIM ANALYSES | 
DATA SAFETY MONITORING PLAN
 
The study only includes children without serious medical illness to reduce the risk of any possible side effects. In addition, melatonin has been studied in children and found to be generally safe and well tolerated. Participants or their family member can report an adverse event via phone, and serious adverse events will immediately be reported to the PI.
 
The PI will promptly judge each AE's impact on the risk/benefit ratio of the study as well as the risk/benefit ratio for each participant as they are reported, so that these ratios will be continuously reassessed throughout the study period. Causality will be determined by the PI for all AEs reported and all AEs will be carefully documented (including AEs determined to be unrelated or only possibly related to the study supplement). AEs will be sent to the DSMB for review at the midpoint and end of study.
 
In the case of an AE occurring that necessitates breaking the blind, the subjects will be discontinued from the study and the data collected before discontinuation will be analyzed as "intent to treat". We have a
 |

| | |
|---|--|

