14 STATISTICAL METHODS AND CONSIDERATIONS

14.1 Data Sets Analyzed

All eligible patients who are randomized and receive at least one dose of the study drug (the Safety Population) will be included in the safety analysis.

[name] will analyze the data using STATA. As a UCSF KL2 Scholar, she will have assistance from the UCSF Dept. of Epidemiology and Biostatistics faculty and CTSI consulting services as needed for statistical issues.

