14.6 Sample Size and Randomization

To detect a difference of 1.1 migraine/migrainous days (SD 1.8) between groups, as was seen in the adolescent topiramate migraine prevention trial that led to FDA-approval of that agent in 12-17 year-olds, we need outcome data on 42 participants/arm. We anticipate that 25% of enrolled participants will be screened out by the single-blind placebo run-in process, and that 85% of those who randomize will complete the trial. Therefore we will enroll 70 per arm, or $n=210$ total.

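### Safety outcome 1b divides by adverse events instead of participants, so as worded it does not measure the risk of a related event per participant

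*Combined protocol and SAP*

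**What the plan says.** Section 14.4 lists the safety outcomes. Outcome 1 is "Proportion with adverse events between groups" and 1a is "Proportion with serious adverse events between groups"; both are shares of participants. Outcome 1b changes form: "Proportion of adverse events thought to be related to the study treatment". Taken literally, numerator and denominator are both events. The synopsis, under other evaluations, words 1b identically.

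Neither document section restates 1b per participant or says how several events in one participant are counted. Section 14.1 defines a participant-based safety set (randomised and at least one dose taken), which 1b as worded does not use.

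Three other provisions bear on the point:

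- Section 14.4 also plans a table of adverse events by treatment group, which "will include the number of patients for whom the event occurred, the rate of occurrence, and the severity and relationship to study drug".
- Safety outcome 2 in section 14.4 compares the mean sleepiness score between arms.
- The synopsis states: "Causality will be determined by the PI for all AEs reported". Sections 9.1.6 and 11.1 have the relationship to study drug recorded for each event.

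**The concern.** A safety reader wants to know how likely a participant in each arm is to have an adverse event attributed to treatment. The literal 1b answers another question: of the events that occurred, what share was attributed to treatment. Its denominator arises after randomisation and can itself be changed by treatment. One participant can also contribute many events. If the three arm values are set side by side in a report, they invite a comparison of risk that the ratio cannot support. Two arms with the same risk can look different, arms with different risks can look the same, and the order can reverse.

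**Working it through.** **Plan's own figure.** There is none to reproduce. The documents give no expected rate of adverse events or related events, and no test or power for 1b.

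**Inputs from the plan.** Section 14.6: "Therefore we will enroll 70 per arm, or $n=210$ total", and "We anticipate that 25% of enrolled participants will be screened out by the single-blind placebo run-in process". Randomised per arm: 70 × 0.75 = 52.5, taken as N = 52. All event counts below are assumptions chosen to show the behaviour of the ratio.

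**Formulas.** Let R be the related events in an arm, U the unrelated events, and P the participants with at least one related event.

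- 1b as written: R / (R + U)
- Risk per participant: P / N

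Neither P nor N appears in the first expression, so it need not follow the second.

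**Step 1: equal risk, more unrelated events.** P = R = 8 (one related event each), so the risk is 8/52 = 15.4% throughout.

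| Unrelated events | 1b as written |
|---|---|
| 12 | 8/20 = 40% |
| 24 | 8/32 = 25% |
| 36 | 8/44 = 18.2% |

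**Step 2: range over the assumed risk.** Compare 12 with 36 unrelated events, at equal risk in both arms.

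| Participants with a related event, each arm | Risk, both arms | 1b, 12 unrelated | 1b, 36 unrelated |
|---|---|---|---|
| 4 | 4/52 = 7.7% | 4/16 = 25% | 4/40 = 10% |
| 8 | 8/52 = 15.4% | 8/20 = 40% | 8/44 = 18.2% |
| 12 | 12/52 = 23.1% | 12/24 = 50% | 12/48 = 25% |

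**Step 3: reversed order.** Arm A has 6 participants with one related event each and 6 unrelated events. Arm B has 9 and 27. Risk is 6/52 = 11.5% against 9/52 = 17.3%, while 1b reads 6/12 = 50% against 9/36 = 25%.

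**Step 4: no movement.** Start from 8 related and 12 unrelated events (8/20 = 40%). Double both, with the added related events in new participants: 1b stays at 16/40 = 40% while risk goes from 8/52 = 15.4% to 16/52 = 30.8%.

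**Step 5: upward movement.** The same 8 participants report 16 related events, with 12 unrelated. 1b becomes 16/28 = 57.1%; risk stays at 15.4%.

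**Step 6: the condition for the downward shift.** Starting from 8/20, add e events of which r are related. The ratio (8 + r)/(20 + e) falls below 40% only if r/e < 0.40. The arm with more events therefore reads lower only when its extra events are judged unrelated more often than those in the other arm.

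**The case against.** Four arguments speak for the plan.

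1. **No comparison is attached to 1b itself.** Outcomes 1 and 1a mention groups; 1b does not. Literally it is a description of events, with no test or contrast. This stands. A reader might infer that the plan commits to an invalid between-arm test on dependent events, and the text does not support that. What remains is that 1b sits in a list of between-group safety outcomes and will naturally be read across arms.

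2. **It may be loose drafting.** As a sub-item of a participant-level outcome, 1b may have been meant as the share of participants with a related event. That is quite possible. The wording still needs correcting, because an analyst who follows it computes a different quantity, and it is the same in both places.

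3. **Other outputs cover much of the ground.** The adverse event table gives patient numbers and relationship by arm. Outcome 1 gives the proportion with any event. Sleepiness, the main expected effect, has its own per-participant score. So one participant's repeated sleepiness reports would not decide how sleepiness is judged. This mitigation is real but incomplete. The table counts patients event by event and does not promise the number with at least one related event. Adding across event types would count a participant with two kinds of related event twice.

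4. **Nothing is decided on 1b.** Section 11.2.1 sends the adverse events themselves to the DSMB, which may stop the study for any safety concern. This stands in full.

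A reader might also infer that an arm with more adverse events will generally look safer on 1b. Steps 4 to 6 show otherwise: the ratio can fall, stay or rise, depending on how the extra events are judged and who has them.

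**Conclusion.** The point holds as a flaw in the definition of one safety outcome, and it is minor. As worded in both places, 1b is a share of events and not the risk of a related adverse event per participant. Under the assumed counts, arms with the same risk of 15.4% read as 40% and 18.2%. Over risks of 7.7% to 23.1%, the pair of values runs from 25% against 10% to 50% against 25%.

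These sizes rest on assumed event counts, on about 52 randomised per arm, and on the ratio being computed literally and compared across arms. They show what the measure can do and do not predict this trial's results. The documents do not support a claim that the safety conclusions as a whole are unreliable. The primary endpoint, the sample size and the DSMB's authority do not depend on 1b.

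**What to change.** In the synopsis and in section 14.4, reword 1b as: *proportion of Safety Population participants with at least one adverse event judged related to study treatment, by arm*. Keep the numbers of events, including repeats within a participant, as description in the planned table.

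The cost is one line in two places and one derived variable per participant. Because the relationship to study drug is recorded for every event, the count needs no new data, visits or participants. The change should be made before unblinding, so that the choice of denominator cannot be linked to the results.

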8 STUDY TREATMENTS

8.1 Method of Assigning Subjects to Treatment Groups

Randomization: 1:1:1 to melatonin 3 mg: 6 mg: placebo. Randomization will be done in blocks of 6 by site. A computer-generated scheme will be used to generate the randomization.

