At the end of the 8-week randomized treatment phase there will be a study completion phone visit. We will again assess the PedMIDAS and CASQ scores. We will query for adverse events, and will solicit participant and parent feedback on the study design. We will remind participants to mail back the study medication bottle using the self-addressed FedEx envelope, and once this is received we will perform both a manual pill count and compare to the self-report count in their diary.

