1. Proportion of participants on melatonin who correctly guessed they were on it (just playing chance, 66% should guess melatonin)
2. Proportion of participants on melatonin who guessed their dose correctly (by chance 50% 3 mg, 50% 6 mg).
3. Proportion of participants on placebo who correctly guessed they were on placebo (by chance, 33% should guess this)
4. The same three above but with investigators guessing.

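### The 66% and 33% chance values for treatment guesses are not a valid reference for blinding; compare guesses between arms instead

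*Combined protocol and SAP*

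**What the plan says.** Section 14.4, under the trial design assessment outcome, lists four items. The synopsis repeats them under Other Evaluations.

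- Item 1: "Proportion of participants on melatonin who correctly guessed they were on it (just playing chance, 66% should guess melatonin".
- Item 2: "Proportion of participants on melatonin who guessed their dose correctly (by chance 50% 3 mg, 50% 6 mg".
- Item 3: "Proportion of participants on placebo who correctly guessed they were on placebo (by chance, 33% should guess this".
- Item 4: "The same three above but with investigators guessing".

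Section 8.1 gives the allocation: "Randomization: 1:1:1 to melatonin 3 mg: 6 mg: placebo". Neither place names a test, a threshold, a blinding index or a comparison of guesses between arms. The documents also do not say whether a guess is forced or whether a participant may answer don't know. This point concerns items 1 and 3 and their investigator versions, not the 50% dose figure in item 2.

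**The concern.** A reference value for blinding should describe what is seen when guesses carry no information about treatment. In that case every arm gives the same mix of guesses, but nothing fixes the mix at two melatonin to one placebo. A participant who knows that two of the three arms are active, and wants to be right as often as possible, always says melatonin. If everyone did so, 100% would be correct on melatonin and 0% on placebo, with blinding intact.

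The protocol itself gives reasons for the mix to drift. Section 2.1 expects a generally high placebo response, and a participant who improves may guess melatonin whatever the arm. One who does not improve may guess placebo.

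Set against 66% or 33%, an arm's correct-guess rate therefore mixes the general tendency to say melatonin with any real unblinding. The migraine-day definition in section 14.3 rests on reported headache severity and symptoms, so readers will look at the blinding result when they weigh a positive finding. The reference value should not mislead them.

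**Working it through.** **1. Reproduce the plan's figures.** With 1:1:1 allocation, the melatonin share is 2/3 = 66.7% and the placebo share 1/3 = 33.3%. A uniform random pick among three labels gives the same values. The documents do not say which reasoning was used.

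**2. What intact blinding implies.** Let g be the probability of guessing melatonin, equal in all arms, with a forced choice. Expected correct rates are g on melatonin and 1 − g on placebo. They equal 2/3 and 1/3 only if g = 2/3.

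**3. Inputs.**
- Numbers guessing: section 14.6 gives 210 enrolled, 25% lost in the run-in and 85% completion. 210 × 0.75 × 0.85 = 133.9, split 2:1 into 89 melatonin and 45 placebo.
- Reading rule (assumed; none is planned): an arm departs from its reference p0 if |p̂ − p0| / √(p0(1 − p0)/n) > 1.96.
- g (assumed; not in the documents): 0.5 to 0.9.

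**4. Thresholds.**
- Melatonin: 0.667 + 1.96 × √(0.2222/89) = 0.765, so 69 or more of 89 correct is above the reference.
- Placebo: 0.333 + 1.96 × √(0.2222/45) = 0.471, so 22 or more of 45 correct is above it.

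**5. Exact binomial probabilities with no unblinding.** Only a rate above the reference would suggest unblinding, so the tails are kept apart.

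| g | Melatonin above 66.7% | Melatonin below | Placebo above 33.3% | Placebo below |
|---|---|---|---|---|
| 0.5 | <0.1% | 90% | 62% | <0.1% |
| 0.6 | <0.1% | 26% | 14% | 0.1% |
| 2/3 | 1.7% | 2.5% | 2.2% | 1.6% |
| 0.7 | 7% | 0.4% | 0.6% | 5% |
| 0.8 | 77% | <0.1% | <0.1% | 44% |
| 0.9 | >99.9% | <0.1% | <0.1% | 97% |

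**6. The alternative.** A two-proportion test of the share guessing melatonin, 89 against 45, flags the same blinded trial about 5% of the time for g from 0.30 to 0.90 (4.7% to 5.1%).

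**7. The reverse error.** Let m and p be the correct-guess rates on melatonin and placebo.
- Forced choice, both arms read: the between-arm difference is m − (1 − p) = m + p − 1. Real unblinding makes m + p > 1, and the two references sum to 1, so at least one expected rate is above its reference. A miss is then only a matter of power. With m = 0.75 and p = 0.45, neither reference is exceeded in 43% of trials; the between-arm test has 65% power.
- One arm read alone: if 66% on melatonin and 40% on placebo guess melatonin, item 1 sits at its reference and exceeds it in about 1% of trials. Item 3, at 60% correct, exceeds its own in 95%.
- Don't-know answers allowed: suppose 60% on melatonin guess melatonin, while on placebo 20% guess melatonin and 30% guess placebo. Neither reference is exceeded in 99% of trials, yet the 40-point difference between arms is detected with power above 0.99.

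**The case against.** The plan lists proportions with a value in parentheses. It sets no alpha and no decision rule, so the error rates above belong to an assumed reading. That stands. But the values are there only to be set against the observed proportions, so some comparison is intended.

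Items 1 and 3 will be reported side by side. Under forced choice the between-arm difference is item 1 plus item 3 minus 1, so a careful reader could recover it, and would see 80% and 20% correct as a general lean towards melatonin. That also stands, and it limits the harm. It does not make the printed references right, and it fails if don't-know answers are allowed.

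Three stronger readings are tempting and are not supported.

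- A reader might count every departure from 66% or 33% as a false sign of unblinding. The 90% for melatonin at g = 0.5 and the 44% for placebo at g = 0.8 lie wholly below the reference. Fewer correct guesses than expected would not be reported as unblinding.
- A reader might infer that the plan can mislead equally in both directions. Missing real unblinding needs one of the two conditions in step 7, or is simply low power.
- A reader might infer that the guess is never collected, because Appendix 1 has no row for it, or that it must be asked at week 4, before the primary window. Appendix 1 also omits PedMIDAS and CASQ, which section 10.5 requires. That section says the study "will solicit participant and parent feedback on the study design", which may include the guess, though it does not say so. A week-4 guess can already reflect perceived benefit and cannot capture unblinding in weeks 5 to 8. The documents do not settle the timing, and no change to it is proposed here.

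**Conclusion.** The 66% and 33% values in section 14.4 and the synopsis are valid only if people happen to guess melatonin two thirds of the time. The correct null is an equal share guessing melatonin in every arm.

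The size depends on g, which the documents do not give. The melatonin figure of about 77% (g = 0.8) and the placebo figure of about 62% (g = 0.5) each concern one arm at one value of g. Near two thirds the problem is small. All of these figures rest on forced choice, the completer numbers implied by section 14.6 and the assumed 5% reading.

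It is a minor correction. The outcome is descriptive, is listed apart from the effectiveness and safety outcomes, and does not enter the primary ANCOVA in section 14.3. A reader might infer that the trial's blinding or its primary result is in doubt; nothing here shows that.

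**What to change.** In section 14.4 and in the synopsis under Other Evaluations:

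1. Delete the 66% and 33% references from items 1 and 3, and so from the investigator items that reuse them.
2. Tabulate guess by arm, for participants and for investigators, showing every response category used, including don't know if it is offered.
3. Report the difference between the melatonin and placebo arms in the share guessing melatonin, with a 95% CI, or Bang's index per arm with its interval.

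The interval will be wide and should be read as such. With 89 and 45 guesses and no unblinding, its half-width is 1.96 × √(g(1 − g)(1/89 + 1/45)), about 14 percentage points at g = 0.8 and 18 at g = 0.5.

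The change needs no new data, visit or question beyond the guesses already listed. The cost is wording in two places and, because the text sits in the protocol, the IRB approval that section 16.1 requires for an amendment.
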